The starting dose of ASP2215 in the dose-evaluation part is 120 mg. According to the Table, at least 3 subjects will receive ASP2215 at the assigned dose (120 mg, or 80 mg as necessary) for the determination of MTD and/or RED. The DLT assessment period for the dose-evaluation part is until the end of induction therapy Cycle 1 and until the end of consolidation therapy Cycle 1 for the dose-expansion part. Subjects who meet any of the

following criteria will be considered unevaluable for DLT and will be replaced by another subject in the cohort.

- A subject that receives less than 80% of the assigned dose of ASP2215 during DLT assessment period specified in each part (e.g., subject in dose assessment part who misses ≥ 3 daily doses during DLT assessment period of dose evaluation part and interrupts the study for a reason other than a DLT)
- Unable to assess the safety adequately during DLT assessment period specified in each part such as due to the lack of required safety assessment(s)

The decision of whether or not to proceed to the next dose of ASP2215 will be made through discussion among the sponsor, principal investigators, and medical advisor with reference to the recommended dose level calculated using Bayesian-CRM, the safety data, etc., and after review by the sponsor's responsible person. The MTD is defined as the highest dose of ASP2215 at which the posterior mean of the DLT incidence during Cycle 1 of induction therapy is estimated to be closest to 33%.

[Phase 2 part]

After achieving the objectives of the Phase 1 part, the Phase 2 part can be initiated. Subjects will receive ASP2215 at the recommended dose established in the Phase 1 part. The primary objective of the Phase 2 part is to evaluate the efficacy of ASP2215 in combination with induction therapy in newly diagnosed FLT3-mutated AML subjects. The target population will be limited to newly diagnosed FLT3-mutated AML. The primary analysis for the primary endpoint of the CR rate will be conducted when all registered subjects complete the induction therapy period.

After treatment discontinuation, subjects will have a 30-day follow-up visit for safety, after which the subjects will enter the long-term follow-up period for collection of subsequent AML treatment, remission status, relapse and survival (cause and date of death). Duration of long-term follow-up is until 3 years after the last subject first treatment or completion of 30-day follow-up of the last subject, whichever is longer.

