- CR/CRh rate after each treatment therapy

CR/CRh: CR or CRh.

Defined similarly as CR rate after each treatment therapy.

- Duration of CR, CR/CRh, CRh, CRc, response

Duration of CR is defined as the time from the date of achieving first CR until the date of first documented relapse for subjects who achieve CR. Subjects who die without report of

relapse are considered non-events and censored at their last relapse-free disease assessment date. Subjects who come off the study for HSCT will be considered non-events and censored at the time of HSCT. Other subjects who do not relapse on study are considered non-events and censored at the last relapse-free assessment date. Duration of CRh, Duration of CR/CRh, Duration of CRc and Duration of response are defined similarly as Duration of CR.

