6.2 Safety Variables

Safety will be assessed by evaluation of the following variables:

- Occurrence of DLTs (Phase 1 part only)
- Adverse events (AEs)

A treatment-emergent adverse event (TEAE) is defined as an AE observed after starting administration of the study drug. If the adverse event occurs on first administration date of the study drug and the onset check box is marked "Onset after first ASP2215 taken" or the onset check box is left blank, then the adverse event will be considered treatment emergent. If the adverse event occurs on first administration date of the study drug and the onset check box is marked "Onset before first ASP2215 taken", then the adverse event will not be considered treatment emergent. If a subject experience an event both before starting administration of the study drug and after starting administration of the study drug, the event will be considered as TEAE only if it has worsened in severity (i.e. it is reported with a new

start date). All adverse events collected that begin within 30 days after taking the last dose of the study drug will also be counted as TEAE, except for subjects that undergo HSCT without leaving the study and plan to resume ASP2215 treatment after HSCT. For these subjects, TEAE is defined as adverse events observed after starting administration of the study drug until the last dose before pre-HSCT visit plus 30 days, and adverse events that begin after resumption of ASP2215 and within 30 days after the last dose of ASP2215 will also be counted as TEAE. Any AEs with onset dates completely missing will be considered TEAEs in summaries. AEs with partially missing onset dates will be assumed TEAEs unless the available portion of the date indicates that the onset was strictly before start of study drug or 30 days after the last dose of study drug. Missing or partial AE onset date will be imputed per Section 7.11.1.

ASP2215-related TEAE is defined as any TEAE with at least possible relationship (possibly or probably related) to ASP2215 as assessed by the investigator or with missing assessment of the causal relationship

A regimen-related TEAE is defined as any TEAE with at least possible relationship (possibly or probably related) to study treatment as assessed by the investigator or with missing assessment of the causal relationship.

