6.5 Other Variables

- FLT3-ITD mutation status
- FLT3-TKD mutation status
- FLT3 mutation status

Either of FLT3-ITD mutation status or FLT3-TKD mutation status is positive, this variable shows positive.

- MRD

MRD negative is defined as summed FLT3-ITD signal ratio of any post-baseline sample $\leq 10^{-4}$. MRD positive is defined as summed FLT3-ITD signal ratio of any post-baseline sample $> 10^{-4}$.

- MR
MR is defined as summed FLT3-ITD signal ratio of any post-baseline sample $\leq 10^{-2}$.
No MR is defined as summed FLT3-ITD signal ratio of any post-baseline sample $> 10^{-2}$.
- FLT3-ITD signal ratio
FLT3-ITD signal ratio is defined as the ratio of FLT3-ITD sequence reads divided by the total number of FLT3 sequence reads. This is being calculated by central laboratory. For subjects with more than one FLT3-ITD variant, the FLT3-ITD signal ratio will be summed at each timepoint.
- Duration of exposure (days)
Duration of exposure to each treatment will be calculated in days, using the following formula:
 - Duration of exposure for each treatment cycle is defined as Last dose date – First dose date + 1 – (on-study HSCT period for subjects undergo on-study HSCT) for each cycle. For Phase1 part, last dose date of study drug exposure = (initial dose date of the cycle + 14 – 1) if last dose date of the cycle is not captured on dosing CRF.
 - Duration of exposure for each treatment period is calculated as sum of the duration of exposure for each treatment cycle.
 - Duration of exposure during study for study drug =
(Duration of exposure for Induction period) + (Duration of exposure for Consolidation period) + (Duration of exposure for Maintenance period).When the last date of exposure is beyond cutoff date, the cutoff date will be used as the last date of exposure. When the start or stop date is missing, then the exposure will be treated as missing.
- Number of dosing days (days)
Defined as number of days with non-zero dosing.
Number of dosing days is calculated for each treatment period.
- Cumulative dose (mg or g)
Defined as total amount of drug given to a patient, which calculated as follows:
 - ASP2215: Sum of (actual dose level * number of dosing days within each dose level)
 - Chemotherapy: Sum of actual dose across the days when administered.
Actual dose is calculated as:
(Actual volume administered / Total volume prepared)* Intended dose * Body surface area.

If number of doses taken is unknown, it will be treated as missing.

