7.4 Analysis of Efficacy

[Phase 1 part]

The efficacy analysis will be performed on the FAS.

For response variables, best response after each treatment therapy period will be summarized. The number and percentage of subjects in each category will be presented together with two-sided exact 95% CIs based on binomial distribution. Swimmer's plot will be presented for response variables.

For time-to-event variables efficacy analysis will be summarized using descriptive statistics. The survival curve and the median will be estimated using the Kaplan-Meier method and will be reported along with the corresponding 95% CIs.

[Phase 2 part]

The efficacy analysis will be performed on the FAS and TTE-FAS. The interpretation of statistical results will be based on the FAS. The TTE-FAS will be used to analyze OS and EFS. Analysis of MRD and MR will be performed using MAS.

Primary efficacy variable

For primary efficacy variable, CR rate after induction therapy period, the two-sided 90% exact CI by Clopper-Pearson method will be calculated. The lower limit will be used to compare with the benchmark of CR rate of 55%. The number and percentage of subjects in each category and swimmer's plot will also be presented. As a supportive analysis, CR rate after induction therapy period reported by Day 60 and CR rate after induction therapy period not being dependent on RBC and platelet transfusion (No Transfusion of RBC and Platelet within 1 week prior to disease assessment) will also be calculated.

Other efficacy variables

For other efficacy variables, analysis method will be described as follows:

Categorical variables:

The number and percentage of subjects in each category will be presented together with two-sided exact 95% CIs based on binomial distribution. Swimmer's plot will be presented for response variables.

For response assessment variables, best response rate after each treatment therapy will be summarized. The number and percentage of subjects in each category will be presented together with two-sided exact 95% CIs based on binomial distribution. For subjects who undergo HSCT, any response assessment data after HSCT will not be used (i.e. for those subjects, only response assessment data before HSCT will be used).

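### Phase 2 duration-of-remission endpoints censor at HSCT only subjects who leave the study for it, so one Kaplan-Meier curve mixes two transplant rules

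*SAP*

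**What the plan says.** Section 6.1.3 defines Phase 2 Duration of CR as time from first CR to first documented relapse, and carries the definition over to CRh, CR/CRh, CRc and response. Relapse is not restricted to the period before transplant. Three censoring rules follow:

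- Deaths without relapse are censored at the last relapse-free assessment.
- For transplant: "Subjects who come off the study for HSCT will be considered non-events and censored at the time of HSCT".
- For everyone else: "Other subjects who do not relapse on study are considered non-events and censored at the last relapse-free assessment date".

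The SAP recognises a second transplant route. Section 6.2 gives a separate treatment-emergent window to "subjects that undergo HSCT without leaving the study and plan to resume ASP2215 treatment after HSCT". Section 6.5 uses the same category for concomitant medication and transfusion, and its exposure formula subtracts the "on-study HSCT period for subjects undergo on-study HSCT".

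Other efficacy rules on HSCT do not separate the routes. The OS sensitivity analysis in 6.1.3 censors all transplanted subjects at HSCT. Section 7.4, under categorical variables, states: "For subjects who undergo HSCT, any response assessment data after HSCT will not be used". It adds a sensitivity analysis that does use those data. The time-to-event paragraph of 7.4 has no HSCT rule.

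**The concern.** The transplant clause depends on leaving the study. A subject who leaves for HSCT stops contributing at transplant, and a later relapse is dropped even though section 3.2 collects relapse in long-term follow-up. A subject transplanted on study is not covered by that clause and falls to the residual one: remission time after transplant counts, and a post-transplant relapse is an event.

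If transplant changes the relapse hazard, the resulting estimate describes neither remission up to transplant nor remission regardless of transplant. It is a blend whose weights are set by how many transplants happened on study. Two cohorts with the same relapse times could report different medians and different 24-month proportions. The SAP plans no HSCT sensitivity analysis for duration that would show the dependence.

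**Working it through.** The SAP states no figure for duration of remission, so there is none to reproduce. The check is a comparison of rules, followed by an illustration of size.

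**Rules side by side**

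| Analysis (SAP section) | Leaves study for HSCT | HSCT on study |
|---|---|---|
| Duration endpoints (6.1.3) | Censored at HSCT | No explicit rule; residual clause, followed through HSCT |
| OS sensitivity (6.1.3) | Censored at HSCT | Censored at HSCT |
| Response rates, main (7.4) | Post-HSCT data not used | Post-HSCT data not used |
| Response rates, sensitivity (7.4) | All data used | All data used |
| RFS (6.1.3) and CIR after CR1 (6.1.4) | No HSCT censoring | No HSCT censoring |

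Only the first row treats the routes differently.

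**Illustration 1 (all inputs assumed).** Relapse hazard is 0.04 per month without HSCT and 0.015 after it. Half the subjects are due for transplant at month 4, if still relapse-free. S(24) is the Kaplan-Meier estimate at 24 months.

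- 0% on study. Every transplant is censored, so only the untransplanted hazard is seen: S(24) = exp(−0.04 × 24) = exp(−0.96) = 0.383.
- 100% on study. Nothing is censored at HSCT. The transplanted half has cumulative hazard 0.04 × 4 + 0.015 × 20 = 0.46, so S(24) = 0.5 × exp(−0.96) + 0.5 × exp(−0.46) = 0.507.
- 50% on study. S(4) = exp(−0.16) = 0.852. After month 4 the untransplanted and the on-study transplanted are at risk in the ratio 0.50 : 0.25, that is 2/3 : 1/3. S(24) = 0.852 × [2/3 × exp(−0.80) + 1/3 × exp(−0.30)] = 0.852 × [2/3 × 0.449 + 1/3 × 0.741] = 0.466.

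The medians at 0% and 100% are 17.3 and 24.6 months.

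**Illustration 2 (all inputs assumed).** Median time to relapse without HSCT is 12 months, transplant falls uniformly between months 2 and 6, and follow-up is 36 months. Each scenario simulates 400,000 responders.

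| Due for transplant | Post-HSCT relapse hazard ratio | S(24), 0% on study | 50% | 100% | Range |
|---|---|---|---|---|---|
| 30% | 0.6 | 0.250 | 0.275 | 0.295 | 4.5 points |
| 60% | 0.6 | 0.250 | 0.313 | 0.338 | 8.8 points |
| 30% | 0.3 | 0.250 | 0.304 | 0.344 | 9.4 points |
| 60% | 0.3 | 0.249 | 0.382 | 0.437 | 18.8 points |

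The 0% column agrees with the closed form exp(−24 × ln 2 / 12) = 0.25. Within each row the relapse process is the same and only study status at transplant differs. With a hazard ratio of 1 the range would be zero.

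**The case against.** **The rule may be deliberate.** The on-study category is tied to a plan to resume ASP2215. Censoring those who end the regimen and following those still on it is a coherent while-on-regimen strategy. This stands far enough that a reader should not infer the split is indefensible. But the SAP does not state that strategy, and 7.4 discards post-HSCT responses for on-study transplants too.

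**The 7.4 exclusion may be meant to cover relapse.** Relapse is defined in 6.1.1 with the responses and from the same assessments. If the exclusion carried over, on-study subjects would be cut at their last assessment before HSCT, and the routes would differ only by the gap to the transplant date. The SAP does not say so: the rule sits under categorical variables and concerns best response. Follow-through for on-study subjects is nevertheless inferred from the residual clause, because no sentence states it.

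**Uncensored views already exist.** CIR after CR1 runs from CR1 to relapse with no HSCT censoring, and is close to Duration of CR without the transplant clause. RFS does something similar for CRc but counts death as an event. This largely stands for CR and partly for CRc. It leaves CRh, CR/CRh and response uncovered, and supplies no version censored for all transplants.

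**The size is assumed, and precision is low.** This stands. At the sample-size assumptions, 70 × 0.70 = 49 subjects reach CR, and a 95% half-width near S = 0.507 is at least 1.96 × √(0.507 × 0.493 / 49) = 0.14. Neighbouring on-study shares would differ by less than that. Imprecision does not settle which quantity is being estimated.

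**Selection.** A reader might infer that on-study transplants go to fitter subjects, making the mix informative as well. The SAP gives no support for this, and the point does not need it.

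**Conclusion.** The point holds as an inconsistency in the definition of five Phase 2 secondary endpoints. As written, HSCT censoring depends on whether the subject leaves the study, on-study transplants have no explicit rule, and each duration curve varies with the on-study share.

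The consequence is limited. These are descriptive Kaplan-Meier summaries in a single-arm study. The CR rate after induction and its comparison with the 55% benchmark are not affected.

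The range of about 5 to 19 points at 24 months rests on assumed relapse hazards, transplant fractions and timing, and on comparing 0% with 100% on study. A reader might take it as the expected bias in this trial. The SAP gives no transplant fraction, on-study share or post-transplant hazard, so it shows only that the effect need not be negligible. Nor do the documents establish that censoring at HSCT must be the main analysis: they support one rule for all, not a particular rule.

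**What to change.** In 6.1.3, replace the transplant clause with one rule for every transplanted subject, on or off study, in all five duration endpoints, and report two versions:

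1. Censored at HSCT for all.
2. Not censored at HSCT for any, with relapse taken from long-term follow-up where it is documented there.

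The sponsor should name the main version before the duration analyses are run. Following the pair in 7.4 would make the censored version main, but either is workable if stated. The text should also say whether the post-HSCT exclusion in 7.4 applies to time-to-event variables.

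The cost is one sentence and one extra run. No new data collection is evident, since the OS sensitivity analysis already needs the HSCT date and section 3.2 already collects relapse. If the censored version is main, some post-transplant follow-up moves to the sensitivity analysis.

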6.1.4 Exploratory Efficacy Endpoints

[Phase 1 part]

- CR rate
Defined as the number of subjects with CR divided by the number of subjects in the analysis population. Subjects with unknown or missing response, or who provide no information on response at the end of study will be treated as non-responders and will be included in the denominator when calculating rates.
- CRp rate
Defined similarly as CR rate.
- CRi rate
Defined similarly as CR rate.
- CRc rate
Defined similarly as CR rate.
- PR rate
Defined similarly as CR rate.
- Overall response rate: CRc + PR
Defined similarly as CR rate.
- Duration of response – Duration of response is defined as the period from the first date of achieving CR, CRp, CRi, or PR to the first date of documented relapse for subjects who achieve CR, CRp, CRi, or PR. Subjects who die without report of relapse are considered non-events and censored at their last relapse-free disease assessment date. Other subjects who do not relapse on study are considered non-events and censored at the last relapse-free disease assessment date.
- Duration of CR is defined similarly as duration of response for subjects who achieved CR.
- Duration of CRc is defined similarly as duration of response for subjects who achieved CRc.

[Phase 2 part]

- Transplantation rate
Transplantation rate is defined as the percentage of subjects undergoing HSCT during the study period.
- Cumulative incidence of relapse (CIR) after 1st CR (CR1)
Defined as the time from the date of achieving CR1 until relapse. When calculating this variable, only subjects who achieved CR1 are included. Subjects alive without relapse will be censored on the date of last relapse-free disease assessment date. Although subjects who died without relapse should be treated as the subjects who occurred competing event, those

subjects will be censored at the date of death.

- Cumulative incidence of death (CID) after CR1

Defined as the time from the date of achieving CR1 until death. When calculating this variable, only subjects who achieved CR1 are included. Subjects who are alive without death will be censored at the date of last known alive.

- Time to hematopoietic recovery after each treatment cycle

Defined as the time from the date of start date of the treatment until the date of having a neutrophil count of $\geq 1,000/\text{mm}^3$ and platelet count of $\geq 100,000/\text{mm}^3$. Subjects with none of these events are censored at the date of last assessment within each treatment cycle.

- MRD

MRD is defined as binary endpoint, negative or positive. More detail of the definition is in Section 6.5. MRD rate is defined as the percentage of subjects whose MRD is negative.

- MR

MR is defined as binary endpoint, MR or no MR. More detail of the definition is in Section 6.5. MR rate is defined as the percentage of subjects who achieve MR.

- MRD-negative CR rate after induction

Defined as the number of subjects who achieve the best response of CR and whose MRD is negative during induction period divided by the number of subjects in the analysis population during induction therapy period. Subjects with unknown or missing response, or who provide no information on response will be treated as non-responders and will be included in the denominator when calculating rates.

- Overall MRD-negative CR rate for any treatment period

Defined as the number of subjects who achieve the best response of CR and at least one post-baseline MRD is negative divided by the number of subjects in the analysis population. If subjects have multiple MRD samples collected across different timepoints, the overall MRD status is negative if there is at least one MRD sample is negative and the overall MRD status is positive if all available MRD samples are positive. Subjects with unknown or missing post-baseline MRD status, or who provide no information on post-baseline MRD status will be treated as MRD positive and will be included in the denominator when calculating rates.

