As a sensitivity analysis, response assessment will be defined similarly as the above analysis, however, all response assessment data will be used even if there were subjects who undergo HSCT (i.e. response assessment data after HSCT will also be used).

Time-to-event variables:

For time-to-event variables efficacy analysis will be summarized using descriptive statistics. The survival curve and the median will be estimated using the Kaplan-Meier method and will be reported along with the corresponding 95% CIs. Kaplan-Meier plot will be presented.

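### Cumulative incidence of relapse after CR1 is computed as one minus Kaplan-Meier with deaths in remission censored, so it overstates relapse and contradicts the SAP's own statement that these deaths are competing events

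*SAP*

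**What the plan says.** All of this concerns the Phase 2 part.

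- **Endpoint (section 6.1.4).** CIR after CR1 is "Defined as the time from the date of achieving CR1 until relapse". The population is restricted: "When calculating this variable, only subjects who achieved CR1 are included".
- **Subjects alive without relapse (section 6.1.4).** "Subjects alive without relapse will be censored on the date of last relapse-free disease assessment date".
- **Subjects who die without relapse (section 6.1.4).** The sentence opens "Although subjects who died without relapse should be treated as the subjects who occurred competing event" and closes by saying that these "subjects will be censored at the date of death". No reason is given for the departure.
- **Estimator (section 7.4, time-to-event variables).** "The survival curve and the median will be estimated using the Kaplan-Meier method and will be reported along with the corresponding 95% CIs". The CIR definition names no estimator of its own, so this general rule governs it.
- **Companion endpoint (section 6.1.4).** Cumulative incidence of death (CID) after CR1 is "Defined as the time from the date of achieving CR1 until death". It is not limited to death before relapse.

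**The concern.** A cumulative incidence of relapse is the probability that a subject in remission has relapsed by a given time, in a world where some subjects die first. A subject who has died in remission can no longer relapse. Censoring that subject makes Kaplan-Meier treat him or her as someone who would have gone on to relapse at the same rate as those still at risk. The resulting curve describes a hypothetical setting without death in remission, and it is too high for the quantity the endpoint is named after.

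The trial would therefore report under the name CIR a figure that makes remission look less durable than it was. It could not be set beside a CIR estimated as a true cumulative incidence function. The SAP also expects transplantation in this population and reports a transplantation rate. The CIR definition has no censoring at transplant, so deaths in remission after transplant would fall under the same rule.

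**Working it through.** The SAP gives no figure for CIR, so there is none to reproduce. The check has three parts.

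**1. Direction, without assumptions.** At each relapse time let d be the number of relapses and n the number at risk.

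- One minus Kaplan-Meier for relapse adds K × d/n, where K is the product of (1 − d/n) over earlier relapses only.
- Aalen-Johansen adds S × d/n, where S is the same product taken over earlier relapses and earlier deaths in remission.

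S contains every factor in K plus one factor below 1 for each earlier death, so S ≤ K. Each step of one minus Kaplan-Meier is at least as large, and it is strictly larger once a death has come before the relapse.

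**2. Size under assumed constant hazards at t = 3 years.** Let a be the yearly relapse hazard and b the yearly hazard of death in remission. Both are assumed. Three years is an illustrative horizon: section 3.2 runs follow-up to at least 3 years after the last subject's first treatment, so time from CR1 varies by subject.

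- Planned method: 1 − exp(−a·t)
- True CIR: a/(a+b) × (1 − exp(−(a+b)·t))
- Death without relapse: b/(a+b) × (1 − exp(−(a+b)·t))

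| a, b | Planned method | True CIR | Death without relapse | Excess (points) | Relative excess |
|---|---|---|---|---|---|
| 0.20, 0.05 | 45.1% | 42.2% | 10.6% | 2.9 | 7% |
| 0.20, 0.10 | 45.1% | 39.6% | 19.8% | 5.6 | 14% |
| 0.30, 0.15 | 59.3% | 49.4% | 24.7% | 10.0 | 20% |

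Example, second row: 1 − exp(−0.60) = 0.451; (0.20/0.30) × (1 − exp(−0.90)) = 0.667 × 0.593 = 0.396.

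These rows contain no low-mortality case. Fixing instead the true 3-year CIR (R) and the 3-year death without relapse (D), constant hazards give a planned result of 1 − (1 − R − D)^(R/(R+D)):

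| R | D = 0% | D = 5% | D = 10% | D = 15% | D = 20% | D = 25% |
|---|---|---|---|---|---|---|
| 20% | 20.0% | 20.6% | 21.2% | 21.8% | 22.5% | 23.3% |
| 30% | 30.0% | 30.9% | 31.8% | 32.9% | 34.0% | 35.3% |
| 40% | 40.0% | 41.2% | 42.6% | 44.1% | 45.7% | 47.6% |

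Example, R = 30% and D = 10%: 1 − 0.60^0.75 = 0.318. For D from 5% to 25% the excess runs from 0.6 to 7.6 points, or about 3% to 19% in relative terms.

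**3. Simulation at about the trial's size.** The number with CR1 was assumed to be 80 × 0.70 = 56, using the enrolment and target CR rate in section 4.1.2. There were 3,000 runs per scenario, with censoring uniform between 3 and 4.5 years.

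| True R, D | Mean, planned method | Mean, Aalen-Johansen | Runs with planned method higher |
|---|---|---|---|
| 30%, 10% | 31.9% | 30.1% | 99.7% |
| 30%, 20% | 34.2% | 30.2% | 100% |
| 40%, 20% | 45.6% | 39.9% | 100% |

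The planned method was lower in no run.

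**The case against.** The strongest reply is about weight.

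- **The endpoint is exploratory.** CIR carries no test, decision rule or sample-size role; the only benchmark comparison is the CR rate against 55%. This stands.
- **The bias may be small beside the sampling error.** With R = 30% and D = 5% it is 0.9 points. With 56 subjects, the 95% half-width around a CIR of 40% is about 1.96 × √(0.40 × 0.60/56) = 0.128, or 13 points, before any loss to censoring. This also stands, but the bias always has the same sign and is avoidable.
- **The bias works against the drug.** It cannot create a false claim of efficacy. True, but the reported relapse figure is still wrong.
- **The censoring is disclosed, and death is covered elsewhere.** Relapse-free survival counts death as an event, and CID reports death after CR1. Disclosure does not turn the curve into a cumulative incidence. Relapse-free survival starts at first CRc rather than CR1, and CID also counts deaths after relapse, so neither supplies the missing piece. As written, CIR comes close to repeating Duration of CR in section 6.1.3, which also censors deaths without relapse.
- **Kaplan-Meier is not named in the CIR definition.** Correct. It comes from the general rule in section 7.4. No other estimator is offered, and a death coded as censored would defeat a competing-risk estimator in any case.

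**Conclusion.** The concern holds. Followed exactly, the SAP produces a one-minus-Kaplan-Meier curve for relapse and labels it cumulative incidence, against its own statement that death without relapse is a competing event. The upward direction is certain and needs no assumption beyond at least one death in remission preceding a later relapse.

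The size cannot be derived from the SAP. Under constant hazards at 3 years it is 0.6 to 7.6 points for a true CIR of 20% to 40% with death without relapse of 5% to 25%. It reaches 10.0 points with assumed hazards of 0.30 and 0.15 per year. This should be corrected, but it does not touch the primary analysis.

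**What to change.** 1. **In section 6.1.4**, replace the censoring of deaths: relapse is the event of interest, death without relapse is a competing event at the date of death, and subjects alive without relapse stay censored as now.
2. **In section 7.4**, add that CIR is estimated with the Aalen-Johansen cumulative incidence function and its 95% CI. SAS 9.4, already named in section 7.1, does this in PROC LIFETEST with the EVENTCODE option.
3. **Report cumulative incidence of death without relapse from the same model.** At every time the two curves then sum to one minus relapse-free survival from CR1. This relapse-free survival differs from the SAP's RFS, which starts at CRc. The present CID, time to any death, can be kept under a name that says so; otherwise CIR and CID count some subjects twice and their sum can exceed 100%.
4. **If the censored curve is kept as well**, label it one minus Kaplan-Meier for relapse, not cumulative incidence.

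The main change costs a sentence and one procedure option. The companion curve needs one more short definition. Relapse and death dates are already collected in long-term follow-up, so no new data are needed. If the SAP is not reissued, section 1 already allows the change to be justified in the clinical study report.
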